Data will be summarized by group and in total. In summary tables of continuous variables, the minimum, maximum, mean, and standard deviation will be presented with one decimal place. We will use counts and percentages in table for categorical variables. The denominator for each percentage will be the number of participants within the group unless otherwise specified. All hypothesis testing will be carried out at a two-tailed Type I error rate of $\alpha = .05$ unless otherwise specified. P-values will be rounded to three decimal places with a minimum of < 0.001 in tables. If statistical methods change during analysis, this will be documented in all reports with justification. Additional analyses of these data will be inevitable, but any exploratory analyses will be clearly marked as such.

Statistical power analysis and sample size selection

IRT and DIF analyses require large samples due to the large number of free parameters to be estimated. The proposed sample size herein is larger than other successful implementations of these same analyses carried out in other IRT studies.¹⁶⁻¹⁹ Moreover, we have carried out computer simulations to determine if our proposed sample sizes will be sufficient to create IRT models. We assumed a one-factor model across two groups at $n = 100$ each with standardized factor loadings set to .7 for eight questionnaire items. We used two groups for this simulation to ensure that any pairwise model comparisons would have adequate power. For this simulation, we specified that a non-significant model χ^2 was a good fit, which is a conservative decision because this particular test is highly sensitive relative to other measures of model fit, especially with large samples. Across 500 iterations, a good-fitting model was identified across groups 90% of the time. Even dropping the sample size to as low as $n = 50$ would identify a good-fitting model 84% of the time.

Missing data

We will describe the rate of missing data on an item-by-item basis using frequency tables in R. We do not anticipate high rates of missing data, but we will conduct subgroup analyses by health literacy, site, and administration mode as need to help diagnose any problems with missing data. For DIF analyses, IRT models

Table 1	
Visit 1 (Baseline)	Description of instrument
Language Assessment	To determine testing in English or Spanish
Single Item Health Literacy Screener	To screen for possible literacy status

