The literature exploring the relationship between overall vaccine hesitancy (not specific to COVID-19 vaccine) has also found conflicting directional relationships between vaccine hesitancy and educational status. Although some studies have found greater vaccine refusal or hesitancy in lower education groups,^{44, 45} others have not.⁴⁶ The relationship between health literacy and vaccine views is also not clear, with studies finding conflicting results.⁴⁷ Health literacy is a potential modifiable factor for vulnerable populations with uncertain vaccination views. We seek to explore the relationship between COVID-19 vaccine hesitancy and health literacy in a diverse participant sample of $N = 300$, who are a subset of the parent study.

Hypothesis: We hypothesize that health literacy is a mediator of the relationship between race/ethnicity and vaccine confidence, such that race predicts health literacy, which is in turn inversely associated with vaccine confidence. Using mediation analysis, we will determine how much of the effect of race/ethnicity on vaccine confidence is mediated by health literacy (i.e., the indirect effect) while also estimating the direct and total effect. A sample of 300 participants will be included in this baseline analysis exploring the relationship between race/ethnicity, health literacy (measured by Health LiTT⁴⁸ obtained at the baseline of the parent study), and the VCI which was administered at follow-up during a period of COVID-19 vaccine approval and early administration. This hypothesis was formulated before looking at any of the data from the phone-based protocol.

Measures:

Demographic Covariates

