Demographic information was collected at the baseline interview. We collected data on age, sex/gender, race and ethnicity, primary language, and education level. The covariates/confounders assessed in our model include age, sex/gender, and education, chosen based on the conceptual model exploring the relationship between health literacy and various health outcomes.⁴⁹ We will report descriptive statistics of demographic variables. To ease interpretation, **Education** will be treated as a dichotomous variable with two categories: high school/GED level education or less versus more than high school education. **Gender** will be treated as dichotomous variable (male/female), because no participants identified as transgender or non-binary in this sample (although our assessment procedures were designed to accommodate non-binary participants). **Age** (in years) will be treated as continuous variable.

Primary Covariate

We will focus on race and ethnicity as primary covariate in our mediation analysis exploring the relationship between race/ethnic status and vaccine confidence. **Race/ethnicity status** will be dummy coded in the following way using white (non-Hispanic) as the reference category:

- X1 =1 if Black/African American (Non-Hispanic); X1=0 otherwise
- X2 = 1 if Latin X/Hispanic Ethnicity; X2=0 otherwise
- X3 = 1 if Other Race/Ethnicity (Non-white); X3 =0 otherwise

The other race category will include participants of mixed race and individuals who identified as Asian, Pacific Islander, or American Indian, categories with fewer participants.

Health literacy: Hypothesized Mediator

Health literacy was measured at baseline using Health Literacy Assessment Using Talking Touchscreen Technology (Health LiTT),⁵⁰ a computerized assessment that does not require an interviewer. This measure has been validated in English and Spanish. We will define **Health Literacy** as a continuous T score obtained from Health LiTT where a higher score is associated with greater degree of health literacy.

Vaccine Confidence Index: Outcome

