The **Vaccine Confidence Index (VCI)** is a tool developed in 2015 that has been used in global samples to measure sentiments correlated with individual confidence around vaccination.^{35,51} The VCI is measured as a ratio of scores on questions that suggest confidence in vaccines divided by scores that indicate suspicion and hesitancy toward vaccination. A larger numerical total score and ratio greater than 1.0 on VCI reflects a greater confidence in pursuing vaccination. **Vaccine Confidence Index (VCI)** will be treated as a continuous variable in the model, with higher numerical values being associated with greater degrees of vaccine confidence.

Primary analysis: Exploring the relationship between vaccine confidence and race/ethnicity status during the COVID-19 pandemic

The analysis plan was formulated and written before any data were analyzed from the phone-based assessment of VCI. We may conduct additional analyses beyond what is described in this plan, but these additional analyses be considered exploratory. We hypothesize that racial or ethnic minority status will be associated with lower levels of vaccine confidence as measured with VCI, controlling for gender, age, and education level. In a theoretical causal pathway for the relationship between race/ethnic demographic status and vaccine confidence we consider race/ethnic minority status as the covariate of interest, and health literacy as a partial mediator of the relationship between race/ethnicity and vaccine confidence. We will use the *lavaan* package in R using regression analyses to compare the estimates of individual, total, direct, and indirect effect estimates for the variables in the model and calculated estimates based on 95% bootstrap confidence intervals for the indirect effect (i.e., X1(race) → lower Health LiTT → lower VCI).

Limitations and Potential sources of Bias

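### The vaccine-confidence addendum predicts opposite directions for the link from health literacy to vaccine confidence, so the plan does not say which sign of the indirect effect supports its mediation hypothesis

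*SAP*

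**What the plan says.** The addendum (SAP, Vaccine Confidence Analysis from phone-based substudy, added 10 March 2021) tests whether health literacy mediates the relation between race/ethnicity and the Vaccine Confidence Index (VCI) in about 300 participants.

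- **Hypothesis paragraph:** "race predicts health literacy, which is in turn inversely associated with vaccine confidence". It gives no sign for the step from race to literacy.
- **Primary analysis paragraph:** the indirect effect is illustrated for the first dummy variable as "X1(race) → lower Health LiTT → lower VCI".
- **Scoring of the mediator** (Health literacy: Hypothesized Mediator): on the Health LiTT T score, "a higher score is associated with greater degree of health literacy".
- **Scoring of the outcome** (Vaccine Confidence Index: Outcome): the VCI is continuous, "with higher numerical values being associated with greater degrees of vaccine confidence".
- **Association of race/ethnicity with VCI** (Primary analysis): "We hypothesize that racial or ethnic minority status will be associated with lower levels of vaccine confidence as measured with VCI", adjusted for gender, age and education.
- **Decision tool:** "95% bootstrap confidence intervals for the indirect effect", with no direction attached. The SAP's general rule (Statistical methodology, Overview) is two-tailed testing at 0.05.

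The addendum says that the hypothesis and the plan were set before the phone-based data were looked at.

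**The concern.** The two paragraphs describe the same path between the same two variables and give it opposite signs. The conflict sits in the formal hypothesis and in the definition of the effect to be tested, not in background text. The background does not settle the matter, because the addendum itself describes earlier findings on literacy and vaccine views as conflicting.

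What is at stake is interpretation. A hypothesis fixed before the data are seen has value because some results would count against it. Here the reader cannot tell which sign of the literacy path counts for the hypothesis and which against. The sign also decides the substantive message: whether low health literacy helps to account for lower vaccine confidence in minority groups, or partly hides it.

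**Working it through.** The addendum gives no effect size or power figure, so there is nothing to reproduce. The check is sign algebra, followed by the size of the two tails.

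**Step 1. Notation.** Let *a* be the effect of minority status (against the non-Hispanic white reference) on Health LiTT. Let *b* be the effect of Health LiTT on VCI, adjusted for race/ethnicity and covariates. The indirect effect is *a × b*, and total effect = direct effect + *a × b*.

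**Step 2. Can coding reconcile the two statements?** Both scales run upward, so an inverse association means *b* < 0, and lower literacy leading to lower VCI means *b* > 0. The choice of race reference group enters *a*, not the sign of *b*. The conflict over *b* therefore stands whatever the coding of race.

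**Step 3. All sign combinations.**

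| *a* | *b* | *a × b* | Hypothesis paragraph (*b* < 0, *a* not stated) | Primary analysis path (*a* < 0, *b* > 0) |
|---|---|---|---|---|
| − | − | + | matches | does not match |
| − | + | − | does not match | matches |
| + | − | − | matches | does not match |
| + | + | + | does not match | does not match |

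If *a* < 0, as the Primary analysis path has it, only the first two rows apply. The two paragraphs then predict opposite signs for the indirect effect, and a non-zero effect of either sign matches one of them. The third row shows that a negative product can also arise by a route that the Primary analysis paragraph does not describe, so stating the sign of *a × b* alone would not be enough.

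**Step 4. Fit with the rest of the addendum.** The predicted total effect of minority status on VCI is negative.

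- With *a × b* < 0 (Primary analysis path), the indirect effect has the same sign as the total. This is ordinary partial mediation.
- With *a* < 0 and *b* < 0 (Hypothesis paragraph), *a × b* > 0. The direct effect, total − *a × b*, is then more negative than the total, and the ratio of indirect to total is negative. That sits badly with the Hypothesis paragraph's own aim of saying how much of the effect is mediated.

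**Step 5. Size.** Suppose *b* = 0. A two-sided 95% interval lies wholly on one given side of zero with nominal probability 1 − Φ(1.96) = 0.025, and on either side with 2 × 0.025 = 0.05. A single stated sign thus leaves a nominal 2.5% chance of apparent directional support, against 5% if either sign could be read as support.

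A percentile-bootstrap simulation at N = 300 gave:

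| Assumed *a* (SD) | Interval below zero | Interval above zero | Either |
|---|---|---|---|
| −0.3 | 1.3% | 1.5% | 2.8% |
| −0.5 | 2.5% | 2.1% | 4.6% |
| −0.8 | 3.0% | 2.8% | 5.8% |

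The simulation inputs are assumptions and do not come from the documents: one binary exposure with 40% prevalence, unit-variance normal errors, a direct effect of −0.2, true *b* = 0, no covariates, and 1000 data sets of 500 bootstrap draws each. The Monte Carlo standard error at 2.5% is √(0.025 × 0.975 / 1000) = 0.005, or 0.5 percentage points.

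**The case against.** **It is probably a slip.** The Primary analysis paragraph is coherent by itself: lower VCI in minority groups, literacy as a partial mediator, lower literacy leading to lower VCI. The text just before the Hypothesis discusses vaccine hesitancy, and an inverse link with hesitancy would agree with that path, so the author may have swapped confidence for hesitancy. This is plausible, and no paragraph describes literacy as a suppressor. But the documents do not prove it, and the slip would sit in the hypothesis sentence itself.

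**Nothing in the analysis changes.** This is correct. The model, covariates, sample, estimate and interval are the same under either reading. The 5% in Step 5 is the two-tailed rate that the SAP declares, so it is not inflation above plan.

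**The analysis is peripheral.** It is an observational mediation analysis in a phone substudy, outside the randomized comparison and the SAP's main analyses of differential item functioning. This limits the importance of the point. The addendum does call it its primary analysis.

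**A reader might infer that no significant result could refute the hypothesis, or that the plan lets either sign count as confirmation.** The documents support neither. A result with *a* > 0 and *b* > 0 matches neither paragraph, and significantly higher VCI in minority groups would contradict the separate prediction about race/ethnicity. The plan nowhere says that either sign confirms the hypothesis, and an author who claimed support from the Hypothesis paragraph's sign would have to disregard the path written in the analysis section.

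**Conclusion.** The contradiction is literal and holds on the text alone: *b* < 0 in the Hypothesis paragraph, *b* > 0 in the Primary analysis paragraph, with both scales scored upward. Given *a* < 0, the predicted sign of the indirect effect reverses completely, and an interval excluding zero on either side would match one written prediction. That consequence depends on *a* < 0, which only the Primary analysis paragraph states, and there for the first dummy alone.

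The defect is one of interpretation, not of estimation or error rate. It should be corrected, because it determines what the addendum can conclude and costs almost nothing to put right. It is not evidence that the authors intend to claim support from either sign.

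**What to change.** Issue a dated correction to the addendum that does four things:

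1. States one direction for the path from literacy to VCI, in the same terms in the Hypothesis and Primary analysis paragraphs. If the path in the Primary analysis paragraph is intended, *inversely* in the Hypothesis paragraph becomes *positively*.
2. Gives the predicted signs of *a*, *b* and *a × b* for each of X1, X2 and X3, or says for which of them no direction is predicted. At present only X1 is illustrated.
3. States that an indirect effect of the opposite sign does not support the hypothesis, even if its 95% interval excludes zero.
4. Says whether the VCI data had been analysed when the correction was made. The documents do not say whether this analysis has been run, and the SAP carries a section added in October 2024, well after the addendum. If results already exist, the report should disclose the discrepancy and the date on which it was resolved.

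The cost is one changed word and a few sentences. No new data, model or sample size is needed.

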This analysis will have several limitations. 1. The sample may not be generalizable as it was restricted to urban and English- or Spanish-speaking participants who consented to participation in a research study. 2. This is a baseline analysis that does not take into the account the potential for changing views on vaccination in the setting of an ongoing pandemic and public health education campaigns. We plan longitudinal analyses in the future to address this limitation. 3. Although we have hypothesized a causal pathway that includes race/ethnicity and health literacy as a partial mediator, we are unable to evaluate alternative pathways for factors that were not measured as part of this study. 4. Mediator-outcome confounding or collider bias is a possibility in this analysis in reference to the variable, educational level, which is related to health literacy and potentially related to the outcome of vaccine confidence. 5. In addition, the possibility of measurement error in the assessment of health literacy not only affects the estimate of health literacy's relationship with vaccine confidence, but also the estimate of the relationship of race or ethnicity with VCI.

Despite these limitations, we feel this analysis adds to the available knowledge on vaccine confidence during the COVID-19 pandemic and opportunities to improve public uptake of vaccination through targeted campaigns and interventions.

Cognitive Correlates of Rumination

Version notes. This plan was added in Version 4.2, 02 June 2021. At the time of the plan, adjust MOCA-B scores had been examined for distributional characteristics and differential item functioning for depression items (DIF; i.e., different measurement properties for PHQ-9 and PROMIS Depression by high-low MOCA-B). Some other analyses of rumination and depression had also been carried out as described in the above section *Prediction of depression: Health literacy as a moderator of rumination, pain, fatigue, and sleep disturbance*.

Sample. The sample will contain all participants ($N = 478$) who completed cognitive measures (see below) recruited into the parent health literacy study before recruitment was stopped due to the COVID-19 pandemic (March 2021). The cognitive measures were administered at one of three time points in the study; corresponding rumination and PROMIS depression measures will be used from the same time point.

Overarching goal

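### Education, the possible confounder the SAP itself names for the vaccine-confidence mediation, is cut to two levels for ease of interpretation, leaving avoidable residual confounding of unknown sign

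*SAP*

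**What the plan says.** The addendum asks how much of the association between race/ethnicity and VCI runs through health literacy. "A sample of 300 participants will be included in this baseline analysis". Under Demographic Covariates it states: "The covariates/confounders assessed in our model include age, sex/gender, and education". Education then "will be treated as a dichotomous variable with two categories: high school/GED level education or less versus more than high school education", and the reason given is "To ease interpretation". Age, in the same paragraph, stays continuous in years. The mediator is also continuous: health literacy is defined "as a continuous T score obtained from Health LiTT where a higher score is associated with greater degree of health literacy".

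The fourth item under Limitations and Potential sources of Bias reads: "Mediator-outcome confounding or collider bias is a possibility in this analysis in reference to the variable, educational level". It describes education as a variable "which is related to health literacy and potentially related to the outcome of vaccine confidence".

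The addendum plans no finer education coding and no sensitivity analysis on the coding. None of its five limitations mentions the loss from dichotomising. Education level was collected at the baseline interview, but the documents do not give the number of levels, their distribution, the share with high school or less, or any correlation with Health LiTT or VCI.

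**The concern.** Education is in the model to remove confounding, and the results of interest are the direct, indirect and total effects of race/ethnicity. A two-level version treats everyone on the same side of the cut as alike: no diploma with a GED, some college with a graduate degree. Health LiTT is continuous and can track those remaining differences. Any effect they have on VCI is then credited to health literacy. The plan names the threat and then coarsens its only control for it, although finer data should be in hand.

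At stake is the coefficient from Health LiTT to VCI. It is one of the two factors in the indirect effect, which is judged by a 95% bootstrap interval.

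**Working it through.** The documents give no residual-confounding figure and no power calculation for this addendum, so there is nothing to reproduce. The only input they supply is n = 300. Everything else below is an assumption.

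**Notation.** E is education at full resolution and D its two-level version. r is the correlation of E with Health LiTT. d² is the squared correlation of E with D. b is the effect of E on VCI in SD units. p is the share with high school or less. Effects are linear, and health literacy has no true effect on VCI.

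**Formulas.**
- Confounding slope with no education adjustment: r·b.
- Slope left after adjusting for D: r·b·(1 − d²)/(1 − r²d²). The share left is therefore (1 − d²)/(1 − r²d²).
- For normally distributed education cut at p: d² = φ(z_p)²/[p(1 − p)].
- Standard error of the literacy path: 1/√[300(1 − r²d²)], with the VCI residual variance set to 1 and no other covariates.
- False-positive rate: the two-sided 5% normal test when the expected z is slope/SE.

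**Near-continuous education.**
- p = .35: φ = .3704, so d² = .1372/.2275 = .603. 
- p = .50: φ = .3989, so d² = .1592/.25 = .637.
- Low corner (p = .50, r = .4, b = .2): share .363/(1 − .16 × .637) = .405; slope .4 × .2 × .405 = .032; SE .061; z = .53; false-positive rate 8.3%.
- High corner (p = .35, r = .6, b = .3): share .397/(1 − .36 × .603) = .507; slope .6 × .3 × .507 = .091; SE .065; z = 1.40; false-positive rate 28.8%.

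| p | r | share left | b = 0 | b = .1 | b = .2 | b = .3 |
|---|---|---|---|---|---|---|
| .50 | .4 | 40% | 5.0% | 5.8% | 8.3% | 12.5% |
| .50 | .6 | 47% | 5.0% | 7.2% | 13.8% | 25.2% |
| .35 | .4 | 44% | 5.0% | 6.0% | 8.9% | 14.0% |
| .35 | .6 | 51% | 5.0% | 7.5% | 15.4% | 28.8% |

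The last four columns are false-positive rates for the Health LiTT to VCI coefficient.

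**Dependence on the form of education** (share of confounding left):
- Normal education, splits 30/70 to 50/50, r = .3 to .6: 38.5% to 53.5%.
- Normal education, 20/80 split, r = 0 to .7: 51% to 67%.
- Four equally spaced levels cut in the middle, r = .3 to .6: 14% to 34%, depending on the distribution.
- Five or six levels, r = .3 to .6: 31% to 47%.
- Education acting only as a step at high school: about 0% (simulated slope .153 unadjusted, .002 after the two-level adjustment).

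**Race in the model.** Simulation with 1,000,000 records, a race term in every model, normal education, splits 30/70 and 50/50 and r = .3 to .6 gave 39% to 57% left after the two-level adjustment. Entering education at full resolution brought the slope to about zero in every case.

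**Sign.** The residual bias takes the sign of the education-VCI association, given that education and literacy rise together. The addendum's background reports conflicting findings on education and vaccine views. The SAP is also inconsistent on the literacy path. The Hypothesis paragraph has health literacy inversely related to vaccine confidence, while the Primary analysis paragraph draws the path from lower Health LiTT to lower VCI. The bias may therefore push the path away from zero or towards it.

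**The case against.** **No size can be read from the documents.** A reader might infer that 40% to 50% of the confounding is known to remain. The documents do not support that: the figure needs near-continuous education, linear effects and a split near the middle. This objection stands, and the size can be given only as a range under stated assumptions.

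**The direction is open.** A reader might infer that the analysis is biased towards showing mediation. That would need a known sign for education's effect on VCI and for the literacy path, and the documents supply neither. If the two have opposite signs, residual confounding pulls the path towards zero. This also stands.

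**The false-positive rates may be mild.** The SAP says only that education may be related to the outcome. With an effect of .1 SD the rate is 5.8% to 7.5%, and with none it is 5%. The 29% is a single corner of the grid. The rates concern the literacy path alone, whereas the planned bootstrap interval for the indirect effect also depends on the race to literacy path. All of this stands as a limit on the magnitude.

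**Interpretability is a stated purpose.** The SAP plans to report estimates for individual variables in the model, so education's coefficient may appear. That is a weak reason to reduce adjustment in the main model, because a two-level summary can be reported alongside it.

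**The problem is disclosed.** The limitation discloses possible confounding, but not that the chosen coding leaves part of it uncontrolled. It also names collider bias. If race/ethnicity affects education, adjusting for education at any resolution changes what the direct and indirect effects mean. Finer coding does not settle that, and neither does a two-level split.

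**Conclusion.** The point holds in a limited form. The plan coarsens the control for a confounder it names itself, for a reason unrelated to confounding, with no check on the consequence. Unless education acts purely as a step at high school, which the SAP does not claim, avoidable residual confounding remains in the Health LiTT to VCI path and in the indirect effect whenever education is related to both variables.

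Across plausible codings about 14% to 67% of the education confounding is left: about 40% to 50% for near-continuous education split near the middle, and about 0% for a pure step. With n = 300, no true literacy effect, near-continuous education split 35/65 or 50/50, and a literacy-education correlation of .4 to .6, the literacy-path false-positive rate is about 6% to 7.5% for a .1 SD education effect and 8% to 29% for .2 to .3 SD. The direction of the bias is undetermined. The change should be made because it is cheap and the data should already exist, although the documents cannot show that the harm is large.

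**What to change.** Enter education at the levels collected, as indicators or an ordinal score, in both the Health LiTT and the VCI equations, merging only sparse categories. Keep the two-level version for descriptive tables or as a sensitivity analysis, and report the indirect effect with its bootstrap interval under both codings. State in the SAP how many education levels were collected and their distribution, so that a reader can judge how much the split discards.

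The cost is a short change of SAP wording and a few degrees of freedom out of 300 participants. Because the addendum presents its plan as written before the VCI data were analysed, a change made after that should be labelled and justified as such. The collider concern in the fourth limitation remains and should stay listed.
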